6.1 Specific Toxicity Management

Dose delays and modifications due to toxicity considered at least possibly related to LY3022855, vemurafenib, and/or cobimetinib will be made as indicated in the following tables. Please also see **6.2** and **6.3** for further guidance on allowed treatment delays and dose modifications:

Table 12: Management of Elevated AST/ALT

Table 12: Management of Elevated 119 1/1121		
AST (SGOT) and/or ALT (SGPT) Increase	Medication Management	
≤ Grade 2	No change.	
Grade 3, increase lasting less than 8 days	Hold study medications until resolution to ≤	
without evidence of other hepatic injury	grade 1 or baseline. Resume study medications	
	at the same dose level.	
Grade 3, increase lasting 8 or more days	Hold study medications until resolution to ≤	
without evidence of other hepatic injury	grade 1; resume study medications with one	
-OR-	dose level reduction.	
Grade 4, without evidence of other hepatic		
injury		
≥ Grade 3, with evidence of other hepatic	Discontinue protocol therapy.	
injury		

Liver transaminase elevations have been associated with all three study medications in previous clinical trials. Patients should be monitored for increases in their liver function tests and for other signs of possible hepatic injury as clinically appropriate and as indicated in the Study Calendar – **Table 23**.

Table 13: Management of Neutropenia

Table 15: Management of Neutropenia		
Neutrophil Count Decrease	Medication Management	
≤ Grade 2	No change.	
Grade 3, no associated fever or infection	Hold study medications until recovery to ≤	
-OR-	grade 2. Upon recovery, restart at the same	
Grade 4, decrease lasting less than 8	dose level.	
consecutive days		
≥ Grade 3, associated with a fever or	Hold study medications until recovery to ≤	
infection	grade 2. Upon recovery, resume with one dose	
-OR-	level reduction.	
Grade 4, decrease lasting 8 or more		
consecutive days		

Table 14: Management of Thrombocytopenia

Platelet Count Decrease	Medication Management
≤ Grade 2	No change.
Grade 3, no clinically significant bleeding	Hold study medications until recovery to ≤ grade 2. Upon recovery, restart at the same dose level.
Grade 3, associated with clinically significant bleeding -OR- Grade 4	Hold study medications until recovery to ≤ grade 2. Upon recovery, resume with one dose level reduction.

Table 15: Management of Rash or Photosensitivity

Tuble 10t Hamingement of Thompson 11th		
Rash or Photosensitivity	Medication Management	
≤ Grade 2	No change.* Implement appropriate supportive	
	care (e.g., topical or oral antibiotics or steroids,	
	use of protective clothing/sunscreen).	
Grade 3, not optimally managed or lasting	Implement appropriate supportive care (e.g.,	
fewer than 8 consecutive days	topical or oral antibiotics or steroids). Hold	
	study medications until recovery to \leq grade 2.	
	Upon recovery, restart at the same dose level.	
Grade 3, optimally managed or lasting 8 or	Hold study medications until recovery to ≤	
more consecutive days	grade 2. Upon recovery, resume with one dose	
-OR-	level reduction.	
Grade 4		

^{*}If a patient is experiencing intolerable grade 2 rash or photosensitivity despite optimal medical management, their study medication may be held at the treating investigator's discretion. Upon resolution to grade 1 or baseline, the study medication can be dose reduced at the treating investigator's discretion.

Table 16: Management of QTc Increase (Associated with Vemurafenib)

QTc Interval Prolonged	Vemurafenib Management
≤ Grade 2	No change.
Grade 3, increase is ≤ 60 msec from pretreatment value	Hold vemurafenib until recovery to ≤ grade 2. Upon recovery, restart with one dose level reduction.
Grade 3, increase is > 60 msec from pre- treatment value -OR- Grade 4	Discontinue vemurafenib.

Table 17: Management of Nausea

Nausea	Medication Management
≤ Grade 2	No change.* Implement appropriate supportive
	care (e.g., antiemetics) as clinically indicated.
Grade 3, not optimally managed	Hold study medication and implement
	appropriate supportive care (including
	antiemetics and IV hydration if indicated).
	Upon resolution to \leq grade 2, resume study
	medication at the same dose level.
≥ Grade 3, optimally managed	Hold study medication until resolution to ≤
-OR-	grade 2; resume study medication with one
Grade 4	dose level reduction if ≥ grade 3 nausea
	persisted for more than 48 hours despite
	maximum supportive intervention.

^{*}If a patient is experiencing intolerable grade 2 nausea despite optimal medical management, their study medication may be held at the treating investigator's discretion. Upon resolution to grade 1 or baseline, the study medication can be dose reduced at the treating investigator's discretion.

Table 18: Management of Vomiting

Vomiting	Medication Management
≤ Grade 2	No change.* Implement appropriate supportive
	care (e.g., antiemetics) as clinically indicated.
Grade 3, not optimally managed	Hold study medication and implement
	appropriate supportive care (including antiemetics and IV hydration if indicated). Upon resolution to ≤ grade 1, resume study medication at the same dose level.
≥ Grade 3, optimally managed	Hold study medication until resolution to ≤
-OR-	grade 1; resume study medication with one
Grade 4	dose level reduction if \geq grade 3 vomiting
	persisted for more than 48 hours despite
	maximum supportive intervention.

^{*}If a patient is experiencing intolerable grade 2 vomiting despite optimal medical management, their study medication may be held at the treating investigator's discretion. Upon resolution to grade 1 or baseline, the study medication may be dose reduced at the treating investigator's discretion.

Table 19: Management of Diarrhea

Diarrhea	Medication Management
≤ Grade 2	No change.* Implement appropriate supportive
	care (e.g., antidiarrheals) as clinically
	indicated.

Diarrhea	Medication Management
Grade 3, not optimally managed	Hold study medication and implement
	appropriate supportive care (including
	antidiarrheals and IV hydration if indicated).
	Upon resolution to \leq grade 1, resume study
	medication at the same dose level.
≥ Grade 3, optimally managed	Hold study medication until resolution to ≤
-OR-	grade 1; resume study medication with one
Grade 4	dose level reduction if \geq grade 3 diarrhea
	persisted for more than 48 hours despite
	maximum supportive intervention.

^{*}If a patient is experiencing intolerable grade 2 diarrhea despite optimal medical management, their study medication may be held at the treating investigator's discretion. Upon resolution to grade 1 or baseline, the study medication may be dose reduced at the treating investigator's discretion.

Table 20: Management of Constipation

Constipation	Medication Management			
≤ Grade 2	No change.* Implement appropriate supportive			
	care (e.g., laxatives) as clinically indicated.			
Grade 3, not optimally managed	Hold study medication and implement			
	appropriate supportive care (including			
	laxatives and enemas if indicated). Upon			
	resolution to \leq grade 2, resume study			
	medication at the same dose level.			
≥ Grade 3, optimally managed	Hold study medication until resolution to ≤			
-OR-	grade 2; resume study medication with one			
Grade 4	dose level reduction if \geq grade 3 constipation			
	persisted for more than 48 hours despite			
	maximum supportive intervention.			

^{*}If a patient is experiencing intolerable grade 2 constipation despite optimal medical management, their study medication may be held at the treating investigator's discretion. Upon resolution to grade 1 or baseline, the study medication may be dose reduced at the treating investigator's discretion.

Table 21: Management of Other Toxicity

Tuble 21: Munu Sement of Other Toxicity							
Other Toxicity	Medication Management						
≤ Grade 2	No change.*§						
≥ Grade 3	Hold study medication. Upon resolution to ≤ grade 2, resume study medication with one dose level reduction. **						
*If a patient is experiencing intolerable grade 2 toxicity, their study medication may be held at							

^{*}If a patient is experiencing intolerable grade 2 toxicity, their study medication may be held at the treating investigator's discretion. Upon resolution to grade 1 or baseline, the study

medication can be dose reduced at the treating investigator's discretion.

**Patients who experience $a \ge grade\ 3$ infusion-related reaction should be discontinued from protocol therapy.

§If a patient is experiencing a new grade 2 or greater increase in CPK, both urine and serum myoglobin laboratory tests should be performed. Additional tests may also be performed or repeated at the treating investigator's discretion.

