5.4 Definition of Dose-Limiting Toxicity (DLT)

Dose-limiting toxicity is based on version 4.03 of the NCI Common Terminology Criteria for Adverse Events (CTCAE). DLT refers to toxicities experienced during the first cycle of treatment that are possibly, probably, or definitely related to the study medication regimen. A DLT will be defined as follows:

- \geq Grade 3 non-hematological toxicity. Exceptions will be made for:
 - Nausea, vomiting, diarrhea, or constipation that can be controlled with appropriate care. Grade 3 and grade 4 nausea, vomiting, diarrhea, or constipation should be considered a DLT if persisting more than 48 hours despite maximum supportive intervention.
 - Grade 3 rash or photosensitivity lasting fewer than 8 days, or that can be controlled with appropriate care. Grade 3 rash or photosensitivity should be considered a DLT if it persists for more than 8 days and cannot be managed despite maximum supportive

intervention.

- Grade 3 thrombocytopenia with clinically significant bleeding
- Grade 4 thrombocytopenia
- \geq Grade 3 febrile neutropenia
- Grade 4 anemia
- Holding of any study medication due to toxicity for a period of greater than 8 consecutive days or two separate periods of any duration during the first cycle.
- Any other significant toxicity deemed by the principal investigator to be dose limiting (for example, any toxicity that is at least possibly related to the study medication regimen that results in the withdrawal of the patient from the study during cycle 1).

Management and dose modifications associated with the above adverse events are outlined in **6.1**, **6.2**, and **6.3**.

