5.6 Criteria for Taking a Participant Off Protocol Therapy

Duration of therapy will depend on individual response, evidence of disease progression and tolerance. In the absence of treatment delays due to adverse event(s), treatment may continue indefinitely or until one of the following criteria applies:

- Disease progression, unless the patient is deriving clinical benefit as agreed upon with the principal investigator
- Intercurrent illness that prevents further administration of treatment
- Unacceptable adverse event(s) including those described in **5.4** and **6.1**
- Participant demonstrates an inability or unwillingness to comply with the oral medication regimen and/or documentation requirements

- Participant decides to withdraw from the protocol therapy
- General or specific changes in the participant's condition render the participant unacceptable for further treatment in the judgment of the treating investigator

Participants will be removed from the protocol therapy when any of these criteria apply. The reason for removal from protocol therapy, and the date the participant was removed, must be documented in the case report form (CRF). Alternative care options will be discussed with the participant.

For Centralized Subject Registrations, the research team submits a completed Off Treatment form to ODQ when a participant comes off study. This form can be found on the ODQ website or obtained from the ODQ registration staff.

For Decentralized Subject Registrations, the research team updates the relevant Off Treatment information in OnCore.

In the event of unusual or life-threatening complications, treating investigators must immediately notify the Overall PI, [name] at DFCI pager number [name].

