6.3 Dose Modifications

The first dose reduction for any toxicity must include a reduction in LY3022855. Further dose reductions will be based on the offending medication(s) according to the schedule outlined in **Table 22**. In the event the treating investigator feels all three medications are responsible for the toxicity, all medications can be reduced. Dose reductions below 25 mg once per week of LY3022855 will not be permitted. Reductions below 480 mg BID of vemurafenib or 20 mg daily of cobimetinib will not be permitted.

A maximum of two dose reductions will be allowed with any one of the medications. If a patient requires more than two dose reductions with any one of the study medications, they should be discontinued from protocol therapy. Exceptions are possible in the event a patient is not tolerating the vemurafenib and/or cobimetinib despite maximal dose reductions but is deriving clinical benefit. In this circumstance, a patient may be allowed to continue on protocol therapy and receive LY3022855 either alone or in combination with just the vemurafenib or cobimetinib if agreed upon with the principal investigator.

Patients undergoing dose reductions for toxicities may not be re-escalated.

Participants enrolled to the phase I portion of the trial may undergo intra-patient dose escalation if subsequent higher dose levels are proven safe as per the guidelines in **5.1** and **5.4**. Participants may only undergo dose escalations to a dose level where ≤ 1 DLT have been observed among 6 patients, two dose levels below a dose level where ≤ 1 out of 3 patients have experienced DLTs, or the dose level that has been declared the RP2D. Under no circumstances may a patient escalate to a dose level above the MTD. Patients must have been on study for at least two cycles with no DLTs or DLT-equivalent toxicity to be eligible for dose escalation.

Table 22: Dose Modifications

Original Dose Level	LY3022855 Reduction	Vemurafenib Reduction*	Cobimetinib Reduction*		
1	1 st Reduction: 25 mg weekly	1 st Reduction: 720 mg BID	1 st Reduction: 40 mg once daily		
	2 nd Reduction: Discontinue protocol therapy	2 nd Reduction: 480 mg BID	2 nd Reduction: 20 mg once daily		
2	1st Reduction: 50 mg weekly	2 nd Reduction: 720 mg BID	1 st Reduction: 40 mg once daily		
	2 nd Reduction: 25 mg weekly	2 nd Reduction: 480 mg BID	2 nd Reduction: 20 mg once daily		
3	1 st Reduction: 75 mg weekly	1 st Reduction: 720 mg BID	1 st Reduction: 40 mg once daily		

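### Table 13 sends grade 4 neutropenia with fever or infection lasting under 8 days to both the same-dose row and the dose-reduction row

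*Combined protocol and SAP*

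**What the plan says.** Section 6.1, Table 13, has two rows for neutropenia of grade 3 or 4. Each row has two alternatives joined by OR.

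- **Same-dose row.** The first alternative is "Grade 3, no associated fever or infection". The second is "Grade 4, decrease lasting less than 8" consecutive days. The action is to hold until grade 2 or lower, then restart at the same level.
- **Reduction row.** The first alternative, printed with a greater-than-or-equal sign in front, is "Grade 3, associated with a fever or" infection. The second is grade 4 lasting 8 or more consecutive days. The action is the same hold, then restart one level lower.

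Three other sections bear on this.

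- **Section 5.4** lists "Grade 3 febrile neutropenia" (again grade 3 or higher) as a DLT when it is related and occurs in cycle 1. It refers management of such events to 6.1, 6.2 and 6.3.
- **Section 6.3** states "The first dose reduction for any toxicity must include a reduction in LY3022855" and "Patients undergoing dose reductions for toxicities may not be re-escalated".
- **Table 22** gives the reduced doses. At dose level 1 a second LY3022855 reduction means stopping protocol therapy.

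**The concern.** The exclusion of fever and infection is attached to the grade 3 line of the same-dose row but not to the grade 4 line. Read literally, a patient with the deeper neutropenia and a fever or infection qualifies for a full-dose restart if the count recovers within 8 days. A grade 3 patient with the same complication does not. The reduction row also covers the grade 4 patient, so the table gives two incompatible instructions for one clinical picture.

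Two clinicians could treat identical patients differently, and each could point to a row that supports the decision. The consequence lasts, because a reduction cannot be undone. At dose level 1 it also uses the only LY3022855 reduction available before protocol therapy must stop. In the other direction, a full-dose restart could follow an event that 5.4 treats as dose-limiting if it is related febrile neutropenia in cycle 1. Infection without fever would be a DLT only through another 5.4 criterion.

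**Working it through.** **Rules as written in Table 13**

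- Same dose = (grade 3 and no fever/infection) or (grade 4 and under 8 days)
- Reduce = (grade 3 or higher and fever/infection) or (grade 4 and 8 days or more)

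**Enumeration** over grade (3, 4), fever or infection (no, yes) and duration (under 8 days, 8 days or more), 2 × 2 × 2 = 8 combinations:

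| Grade | Fever/infection | Duration | Row(s) met as written | After the fix |
|---|---|---|---|---|
| 3 | no | < 8 d | same dose | same dose |
| 3 | no | ≥ 8 d | same dose | same dose |
| 3 | yes | < 8 d | reduce | reduce |
| 3 | yes | ≥ 8 d | reduce | reduce |
| 4 | no | < 8 d | same dose | same dose |
| 4 | no | ≥ 8 d | reduce | reduce |
| 4 | yes | < 8 d | **both** | reduce |
| 4 | yes | ≥ 8 d | reduce | reduce |

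As written: 3 same dose + 4 reduce + 1 both = 8, with none uncovered. After the fix: 3 same dose + 5 reduce = 8. Table 13 does not itself split grade 3 by duration. Collapsing those rows leaves 6 cells, of which the same single cell conflicts.

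**Which row was meant.** Suppose the first alternative of the reduction row applied to grade 3 only. Grade 4 with fever or infection lasting 8 days or more would still be reduced under the second alternative. The only combination lost would be grade 4, fever or infection, under 8 days. So the greater-than-or-equal sign has an effect only if this combination is meant to be reduced.

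**Neighbouring tables.** Table 12 repeats its hepatic-injury qualifier on every grade 3 and grade 4 line. Table 14 puts all grade 4 thrombocytopenia in the reduction row. Neither has this overlap, which suggests an omission in Table 13.

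**Size of the dose difference** (LY3022855, first reduction from the original level, Tables 10 and 22):

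| Dose level | Same dose | Reduced | Difference | Four infusions |
|---|---|---|---|---|
| 1 | 50 mg | 25 mg | (50 − 25)/50 = 50% | 200 vs 100 mg |
| 2 | 75 mg | 50 mg | (75 − 50)/75 = 33% | 300 vs 200 mg |
| 3 | 100 mg | 75 mg | (100 − 75)/100 = 25% | 400 vs 300 mg |

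The gap is 25 mg per infusion, or 4 × 25 = 100 mg over a cycle in which all four infusions are given. Under 6.2, infusions missed during a hold are skipped, so the gap in a given cycle can be smaller.

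**The case against.** The strongest reply is that the table has one sensible reading. The reduction row expressly includes grade 4 with fever or infection, and reading the duration-only line as overriding it would leave part of that row without effect. On this view the same-dose line cannot be read alone, and the table as a whole does not plainly allow a full-dose restart. The point about intent stands. But the reader has to infer it, because sections 6.1 to 6.3 contain no rule of precedence.

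Other text might settle the matter:

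- **Table 21** tells sites to "resume study medication with one dose level reduction" after other toxicity of grade 3 or higher. Febrile neutropenia recorded as a separate event could fall there. That supports a reduction but does not decide the case. Table 13 has its own line for neutropenia with fever or infection, and Table 21 does not reduce for a fever or infection below grade 3.
- **Section 5.6** lists "Unacceptable adverse event(s) including those described in" 5.4 and 6.1 as a ground for removal, and says participants will be removed when a criterion applies. Whether an event is unacceptable remains a judgement. Section 5.4 sends its own events to the dose-modification rules, so some of these patients are expected to continue. For them 5.6 sets no restart dose.

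A further objection is that the trigger is probably rare. Section 2.2.2.4 does not list neutropenia among the related events of grade 3 or higher in JSCA (29 patients) or the related grade 3 events in JSCB (14 patients). Section 7.1 names lymphopenia, not neutropenia, among anticipated serious events. That is fair, although single-agent data do not fix the rate for the triplet. A count of combinations is likewise not a frequency. These points keep the matter minor; they do not remove the overlap.

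**Conclusion.** The concern holds. Table 13 is wrong as written for exactly one combination: grade 4 neutropenia with fever or infection lasting under 8 days. Reduction is evidently the intended action. Only the restart dose is affected, since the hold is identical in both rows. DLT counting, the MTD rule, power, type I error and endpoints do not change.

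The LY3022855 difference of 50%, 33% or 25% assumes a first reduction from dose level 1, 2 or 3. In phase II only the level chosen as the RP2D is relevant. No number of affected patients is claimed, because the documents give no event rate for the triplet. This is a low-priority correction, worth making because it concerns a dosing instruction after a serious toxicity.

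**What to change.** In the same-dose row of Table 13, give the grade 4 line the exclusion that the grade 3 line already has, for example: *Grade 4, without associated fever or infection, lasting less than 8 consecutive days*. Every combination then meets exactly one row. Sections 5.4 and 5.6 and Table 21 need no change.

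The cost is one phrase in one table line at the next amendment, with no effect on sample size or any other statistical feature of the design.

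### Table 15's two grade 3 rash rows overlap, so two of the four combinations of management and duration call for both the same dose and a dose reduction

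*Combined protocol and SAP*

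**What the plan says.** Section 6.1, Table 15, has two rows for grade 3 rash or photosensitivity. Both hold study medication until recovery to grade 2 or lower; they differ in the dose at restart.

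- **Same-dose row.** The condition is "Grade 3, not optimally managed or lasting" "fewer than 8 consecutive days". The instruction is "Upon recovery, restart at the same dose level".
- **Reduction row.** The condition is "Grade 3, optimally managed or lasting 8 or" more consecutive days, or grade 4. The instruction reads "grade 2. Upon recovery, resume with one dose" level reduction.

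The table's only footnote gives the investigator discretion over intolerable grade 2 rash. It does not address grade 3.

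Section 6.3 fixes what a reduction means: "The first dose reduction for any toxicity must include a reduction in LY3022855", and "Patients undergoing dose reductions for toxicities may not be re-escalated". Table 22 gives the first LY3022855 step for each original dose level: 50 to 25 mg weekly at level 1, 75 to 50 mg at level 2, and 100 to 75 mg at level 3. At level 1 the second LY3022855 step is discontinuation of protocol therapy.

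Section 5.4 deals with rash separately for DLT purposes. Its general rule makes any non-hematological toxicity of grade 3 or higher a DLT. It then exempts grade 3 rash that lasts under 8 days or can be controlled, and adds: "Grade 3 rash or photosensitivity should be considered a DLT if it persists for more than 8 days and cannot be managed".

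**The concern.** A dose-modification table should send each event to one instruction. Here both grade 3 rows link two criteria with *or*. The logical complement of *A or B* is *not A and not B*, so a second row that again uses *or* cannot be the complement of the first. Some rashes must then meet both rows and receive opposite instructions.

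What is at stake is consistent exposure to the investigational drug. The row chosen decides whether LY3022855 is permanently reduced, and the safety and efficacy results are meant to describe a regimen at a stated dose. With 6 to 18 patients in phase I and 25 in phase II (section 13), even a few discordant decisions could be visible in the exposure data. The situation is foreseeable, since section 5.5 notes that photosensitivity has occurred with both vemurafenib and cobimetinib.

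**Working it through.** The plan states no figure on this point, so the check is a truth table.

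**Inputs.** Let M mean that the rash was optimally managed, and let L mean that it lasted 8 or more consecutive days. From Table 15, for grade 3:

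- Same-dose row applies if (not M) or (not L).
- Reduction row applies if M or L.

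**Enumeration.**

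| Optimally managed | Duration | Same-dose row | Reduction row | Result |
|---|---|---|---|---|
| Yes | under 8 days | applies | applies | conflict |
| Yes | 8 days or more | no | applies | reduce |
| No | under 8 days | applies | no | same dose |
| No | 8 days or more | applies | applies | conflict |

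Two of the four combinations meet both rows, and none meets neither. Grade 4, and grade 2 or lower, are unaffected.

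**Is there a tie-breaker?** Sections 6.1, 6.2 and 6.3 give no order of precedence between rows. Neighbouring tables avoid this particular overlap by using one criterion: Table 12 splits grade 3 transaminase elevation without other hepatic injury by duration alone, and Tables 17 to 20 split grade 3 events by management alone.

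**Size of the divergence per patient** (Table 22, first LY3022855 step):

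- Level 1: (50 − 25)/50 = 50%
- Level 2: (75 − 50)/75 = 33%
- Level 3: (100 − 75)/100 = 25%

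**Effect of changing the connectives.** Changing *or* to *and* in exactly one of the two rows makes them mutually exclusive and exhaustive. If it is changed in the same-dose row, both disputed combinations go to reduction; if in the reduction row, both go to the same dose. Changing it in both rows leaves the two disputed combinations with no instruction at all.

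**Section 5.4 at exactly 8 days.** A grade 3 rash of exactly 8 days that cannot be controlled is outside the exemption, which needs under 8 days or control. It is also not named by the sentence that requires more than 8 days. The general rule for grade 3 or higher non-hematological toxicity still applies, so such a rash, if at least possibly related to the regimen and in cycle 1, is a DLT. Its status is settled; only the two duration phrases fail to meet.

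**The case against.** The strongest reply is that the practical effect is small. Two of four is a count of table cells, not of patients, and the documents give no rate of grade 3 rash from which to estimate how many are affected. One of the two conflicting cells may also be rare: the same-dose row itself orders supportive care, and LY3022855 is given weekly, so a grade 3 rash should seldom stay poorly managed for 8 days or more. The optimally managed, short-lived rash is the more realistic conflict. These points limit the size of the problem. They do not remove the contradiction, and nothing in sections 6.1 to 6.3 resolves it.

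A reader might infer three stronger things that the documents do not support.

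- **That the overlap blurs DLT classification.** DLT status is set by section 5.4, which has no criterion based on dose reduction. It does count a hold of more than 8 consecutive days, or two separate holds, in cycle 1. Both Table 15 rows order the same hold, so choosing one row over the other does not in itself change DLT status.
- **That reducing the dose for a rash that is not a DLT is itself a contradiction.** A DLT criterion and a dose-modification rule serve different purposes and need not coincide. Table 13, for example, reduces the dose for grade 4 neutropenia of 8 or more days, whereas the neutropenia criterion listed in 5.4 is febrile neutropenia. The two sections also use different terms: in Table 15, optimal management is best read as the care given, while control in 5.4 is the result of care. The use of *and* in 5.4 against *or* in Table 15 is therefore not an error by itself.
- **That an uncontrolled grade 3 rash of exactly 8 days has no DLT status.** As shown above, the general grade 3 rule covers it.

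**Conclusion.** The point holds for Table 15. Its grade 3 rows contradict each other for two of the four combinations of management and duration, and no precedence rule exists. For a patient in either combination, the reading chosen leads to a lasting LY3022855 difference of 25, 33 or 50% of the assigned weekly dose, at levels 3, 2 and 1 respectively. The 50% figure is specific to level 1, where the reduction also uses up the only step before discontinuation of protocol therapy.

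This rests on reading the two rows literally and on section 6.3 applying to rash as to any other toxicity. How many patients would be affected, and any effect on PFS or the safety results, cannot be estimated from the documents. The risk lies in different investigators reading the same table differently; the protocol marks sites outside DF/HCC as not applicable. The point merits correction at the next amendment. The unmatched duration phrases in the 5.4 rash bullet are a minor wording matter.

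**What to change.** Reconcile the two grade 3 rows of Table 15 so that every grade 3 rash or photosensitivity event falls in exactly one. The clinical team should decide which instruction applies to which group; this review takes no view on that. Before release, test the new wording against all four combinations, because simply replacing *or* with *and* in both rows would turn the two conflicts into two omissions.

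At the same time, as a minor tidy-up, align the two duration phrases in the 5.4 rash bullet so that they meet at day 8. There is no need to make Table 15 and section 5.4 identical.

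The cost is one table and one bullet reworded in an amendment, with no added patients or procedures.
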